5.2.2.3.1. Supplementary Estimator 1 (ITT Analysis Set + MI)

For this supplementary estimator, the same estimand defined in Section 5.2.2, statistical model (MCP-Mod, and stratum-adjusted MH test), assumptions and approach to control the Type I error rate, and the same MI rule to handle missing data will be used as for the main estimator (Section 5.2.2.1).

5.2.2.3.1.1. Data Included

All available data from ITT analysis set, after taking into account all the intercurrent events and applying the intercurrent event strategies specified in Section 5.2.2, will be included.

5.2.2.3.1.2. Supplementary Estimator 2 (ITT Analysis Set + LOCF)

For this supplementary estimator, the same estimand defined in Section 5.2.2, statistical model (MCP-Mod, and stratum-adjusted MH test), assumptions and approach to control the Type I error rate will be used as for the main estimator (Section 5.2.2.1). For Mod-step, model averaging techniques across the statistically significant candidate models obtained from the MCP step will be used to derive the dose-response shape (Mod step).

The missing data approach will follow the LOCF approach as described in Section 5.2.2.2.2.

5.2.2.3.1.3. Supplementary Estimator 3 (ITT Analysis Set + Tipping Point)

For this supplementary estimator, the same estimand defined in Section 5.2.2, statistical model (MCP-Mod, and stratum-adjusted MH test), assumptions and approach to control the Type I error rate will be used as for the main estimator (Section 5.2.2.1).

This supplementary estimator will use the tipping point approach as described in Section [5.2.2.2.3](#).

5.2.3. Supplementary Estimand 1 (Missing as Non-Response)

A) Study Intervention:

- Arm 1: JNJ-3989 (100 mg) + JNJ-6379 (250 mg qd) + NA
- Arm 2: JNJ-3989 (200 mg) + Placebo + NA
- Arm 3: JNJ-3989 (100 mg) + Placebo + NA
- Arm 4: JNJ-3989 (40 mg) + Placebo + NA
- Arm 5: Placebo + JNJ-6379 (250 mg qd) + NA
- Arm 6: Placebo + Placebo + NA

B) Study Population: HBeAg-positive and -negative chronic HBV-infected patients who are not being treated for their HBV infection (including treatment-naïve participants) or are virologically suppressed by NA treatment.

C) Variable: Response status defined as meeting the NA treatment completion criteria (responders) at Week 48 as defined in Section [5.2.1](#).

D) Intercurrent events:

- Treatment discontinuation prior to Week 48: if the participant discontinued treatment prior to Week 48 s/he will be considered as non-responder (composite strategy).
- Major protocol deviations affecting efficacy: [ATTACHMENT 1](#) identifies the deviations considered intercurrent event (Per Protocol set 1 [PP1] for the primary efficacy endpoint). Participants with such deviations and who have missing data for the primary endpoint at Week 48 will be considered as non-responders (composite strategy).
- Deaths prior to Week 48 are handled in a composite strategy as participants who die prior to Week 48 will be considered as non-responders.

E) Population-level summary: Difference in proportion of responders at Week 48 between study intervention arms.

5.2.3.1. Main Estimator

5.2.3.1.1. Analysis Methods

Statistical Model

The same MCP-Mod approach and stratum-adjusted MH test on the difference of proportions as described for the main estimator of the primary estimand will be used (see Section [5.2.2.1](#)).

For Mod-step, model averaging techniques across the statistically significant candidate models obtained from the MCP step will be used to derive the dose-response shape (Mod step).

5.2.3.1.2. Data Included

All available data from mITT analysis set, after taking into account all the intercurrent events and applying the intercurrent event strategies specified in the previous Section 5.2.3, will be included.

An additional analysis of this estimand will be performed using the ITT analysis set, after taking into account all the intercurrent events and applying the intercurrent event strategies specified in the previous Section 5.2.3, will be included.

5.2.3.1.3. Assumptions

- Missing Data for ALT, HBV DNA, and HBsAg are missing not at random
- The treatment effect is homogeneous across strata

5.2.3.1.4. Missing Data Handling Rule

Participants who withdraw from the study prior to Week 48 will be considered as non-responders. All participants with missing data for the determination of the primary endpoint status will be imputed as non-responders.

5.2.4. Supplementary Estimand 2 (Per-Protocol Analysis Set)

A) Study Intervention:

- Arm 1: JNJ-3989 (100 mg) + JNJ-6379 (250 mg qd) + NA
- Arm 2: JNJ-3989 (200 mg) + Placebo + NA
- Arm 3: JNJ-3989 (100 mg) + Placebo + NA
- Arm 4: JNJ-3989 (40 mg) + Placebo + NA
- Arm 5: Placebo + JNJ-6379 (250 mg qd) + NA
- Arm 6: Placebo + Placebo + NA

B) Study Population: HBeAg-positive and -negative chronic HBV-infected patients who are not being treated for their HBV infection (including treatment-naïve participants) or are virologically suppressed by NA treatment and who are able to tolerate the treatment regimen and will comply with the treatment schedule as prescribed.

C) Variable: Response status defined as meeting the NA treatment completion criteria (responders) at Week 48 as defined in Section 5.2.1.

D) Intercurrent events:

- Treatment discontinuation prior to Week 48: if the participant discontinued treatment prior to Week 48 s/he will be considered as non-responder (composite strategy).
- Deaths prior to Week 48 are handled in a composite strategy as participants who die prior to Week 48 will be considered as non-responders.

E) Population-level summary: Difference in proportion of responders at Week 48 between study intervention arms.

5.2.4.1. Main Estimator

5.2.4.1.1. Analysis Methods

Statistical Model

Similar MCP-Mod and stratum-adjusted MH test on the difference of proportions as described for the main estimator of the primary estimand will be used (see Section 5.2.2.1).

5.2.4.1.2. Data Included

All available data from randomized participants that are included in the PP1 analysis set will be used, after taking into account the intercurrent events and applying the intercurrent event strategies specified in Section 5.2.4.

To complement this analysis because of its inherent bias and allow a better interpretation of the results, the proportions of participants excluded from the PP1 analysis set will be summarized by intervention arm and by type of major protocol deviation.

5.2.4.1.3. Assumptions

- The treatment effect is homogeneous across strata

5.2.4.1.4. Missing Data Handling Rule

Participants who withdraw from the study prior to Week 48 will be considered non-responders. For the participants still in the study at Week 48 or for participants that have neither discontinued treatment early nor experienced any major protocol violations as listed in [ATTACHMENT 1](#) (PP1 column), but ALT, HBV DNA, and/or HBsAg values missing at Week 44, then the primary method to handle missing data will be the imputation to non-responder.

5.2.5. Subgroup Analyses of Primary Efficacy Endpoint

The potential association between the primary endpoint and the randomization stratification factors will be explored by a multivariate logistic regression model and exploration of the interaction terms using observed case data. The model will include intervention arm, treatment history and HBeAg status at screening, as factors, and the intervention arm-by-treatment history and intervention arm-by-HBeAg status interaction terms. If the model does not converge, then the interaction term may be removed from the model as a means to facilitate model convergence. The primary endpoint estimates for each intervention arm will be derived from this model and presented graphically with their 90% CI in a forest plot.

In addition, for assessment of internal consistency and investigation of homogeneity of the treatment effect in the primary efficacy endpoint across other subgroups (as defined in Section 2.4.1), similarly to what is described above, a multivariate logistic regression model ([Brooks ST. et al., 2004](#)) will be estimated for each subgroup variable at a time. The factors in the model will be intervention arm, treatment history, HBeAg status at screening and the subgroup

variable as factors, and the intervention arm-by-subgroup variable as the interaction-term (Brooks ST. et al., 2004). Corresponding 90% CIs will be also calculated without multiplicity adjustment for each intervention arm. Statistical analysis of treatment heterogeneity between subgroups will be conducted by assessing the significance of the interaction term. The forest plot will present graphically the primary endpoint estimate, its 90% CI resulting from the model across intervention arms by the prespecified subgroups.

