5.2.2.1. Main Estimator

5.2.2.1.1. Analysis Methods

5.2.2.1.1.1. Scientific Question Part a: JNJ-3989 Dose Response Trend Test and Dose Response Model Estimation

[figure not shown]
Statistical Model: For the JNJ-3989 dose-finding objective, a hybrid methodology that combines aspects of multiple testing with modeling techniques (MCP-Mod) will be used for evaluating a dose-response trend and estimating the dose-response relationship of 3 JNJ-3989 doses in combination with NA (Arm 2, 3 and 4) versus NA treatment alone (control Arm 6). Because the primary efficacy endpoint is binary, the generalized MCP-Mod approach ([Pinheiro J. et al, 2014](#)) will be used on the logit scale. Following the notation in Pinheiro et al (2014), the “dose-response parameter” estimates and their variance-covariance matrix will be obtained from a logistic regression with JNJ-3989 dose treated as a factor, where Arm 6 corresponds to “JNJ-3989 dose=0

mg”. The Firth's penalized likelihood method (Firth D., 1993 & Heinze G. et al., 2002) will be used in the logistic regression to reduce possible bias which could arise in the presence of a zero response rate at one or more dose levels

If one or more prespecified models are found to be significant (multiple contrast test approach), a significant trend test among Arms 2, 3, 4, and 6 (JNJ-3989 40 mg, 100 mg and 200 mg and NA control), under the null hypothesis of no differences across the 4 arms will be declared.

A set of 5 candidate models (see [Figure 1](#)) was prespecified as possible dose-response shapes in terms of the logit of the primary efficacy endpoint. The 5 candidate models are the EMax1 (ED₅₀=5 mg), EMax2 (ED₅₀=100 mg), Linear, Exponential (d=40) and Sigmoid Emax model (ED₅₀=110 mg, h=8). A dose-response trend is established when the maximum of the t-test statistics exceeds the critical value at the one-sided 0.05 alpha.

Figure 1: Candidate Dose-response Models on the Logit Scale

Characterization of the dose-response model: The model averaging techniques (Bornkamp B. et al., 2009) across the candidate models will be utilized to derive the dose-response shape and to evaluate the desired dose(s) of JNJ-3989 (modeling step). The estimated dose response curve and the corresponding 90% confidence band will be plotted against the JNJ-3989 dose range of 0 mg to 200 mg.

5.2.2.1.1.2. **Scientific Question Part b: Pairwise Comparisons vs Control Arm**

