5.2.2.2.1. Sensitivity Estimator 1 For the Main Estimand (Homogeneity Assumption)

Homogeneity will be assessed for scientific question part b, comparison vs control arm. For this sensitivity estimator 1, the same included data, missing data assumption (MAR), and missing data handling rule (multiple imputation) as well as the same approach to control the Type I error rate (Section 5.1.1) will be applied. The assumption for homogeneity of treatment effect across the stratification factors will be tested and, if heterogeneity is found statistically significant, a different statistical model is used to define the sensitivity estimator.

5.2.2.2.1.1. Assumptions

- Missing Data for HBV RNA, ALT, and HBsAg are Missing at Random
- The treatment effect is non-homogeneous across strata

5.2.2.2.1.2. Analysis Methods

Homogeneity of treatment effect for each stratification factor separately will be tested using the weighted least squares chi-squared statistic (Lui K. J. et al., 2000) for one-way homogeneity. Tests of homogeneity will be assessed at the one-sided 10% level of significance.

Any heterogeneity found to be statistically significant will be explored using the following statistical model for the sensitivity estimator 1.

Statistical model: A logistic regression model on the primary efficacy endpoint using the 2 randomization stratification factors and interaction terms. The model will include intervention arm, treatment history status and HBeAg status at screening as factors, and the intervention arm-by-factor interaction terms.

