5.3.6. Subgroup Analyses of The Key Secondary Endpoint

The potential association between the functional cure rate and the randomization stratification factors will be explored by a multivariate logistic regression model and exploration of the interaction terms using observed case data. The model will include intervention arm, treatment history and HBeAg status at screening, as factors, and the intervention arm-by-treatment history and intervention arm-by-HBeAg status interaction terms. The functional cure estimates for each intervention arm will be derived from this model and presented graphically with their 90% CI in a forest plot. In addition, for assessment of internal consistency and investigation of homogeneity of the treatment effect in functional cure across other subgroups (as defined in Section 2.4.1), the same logistic regression approach as defined in Section 5.2.5 will be used.

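### SAP 5.2.5 lets the interaction be dropped when a subgroup logistic model does not converge, which removes the term that tests heterogeneity; Firth's method, already in the SAP, would keep it

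*SAP*

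**What the plan says.** SAP 5.2.5 fits two kinds of logistic model to the primary endpoint. The first has arm, treatment history, HBeAg status and the two arm-by-factor interactions. The second is fitted once for each other variable in Section 2.4.1, "similarly to what is described above, a multivariate logistic regression model", with that variable and its interaction with arm.

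The interaction carries the inference: "Statistical analysis of treatment heterogeneity between subgroups will be conducted by assessing the significance of the interaction term". The display depends on the same fit: "The forest plot will present graphically the primary endpoint estimate, its 90% CI resulting from the model across intervention arms by the prespecified subgroups". The fallback is: "If the model does not converge, then the interaction term may be removed from the model as a means to facilitate model convergence". The amendment history explains that this sentence came in with Amendment 2, because some subgroup models had failed to converge and taking the interaction out had resolved it.

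For functional cure in the other subgroups, SAP 5.3.6 says "the same logistic regression approach as defined in Section 5.2.5 will be used".

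Elsewhere the SAP already plans for empty cells. In the MCP-Mod analysis (5.2.2.1.1.1), Firth's penalised likelihood "will be used in the logistic regression to reduce possible bias which could arise in the presence of a zero response rate" in any dose group. It is not named in 5.2.5 or 5.3.6.

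Protocol 9.4.1.1 plans to judge each intervention-by-stratification-factor interaction by comparing fits with and without it. Protocol Section 3 lists the influence of HBeAg and treatment status on response as an exploratory objective.

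**The concern.** The term that may be dropped is the term under test. If the full model fails, the comparison in protocol 9.4.1.1 cannot be made, and the forest plot shows estimates from a model that assumes the same odds ratio in every subgroup. Nothing in 5.2.5 requires such a panel to be marked, so a reader could take smoothed estimates for evidence of consistency.

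The trigger is also not neutral. These models tend to fail where an arm has no responders in a subgroup, and that is where a difference between subgroups may be largest. Control response is expected to be low and Arm 6 is small, so the situation should be common.

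Two details are open. The SAP does not define non-convergence. The sentence also refers to a single interaction in a paragraph that lists two, so it is unclear which would go.

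**Working it through.** The plan gives no probability of non-convergence, so there is none to reproduce. As a check on how arm sizes and rates are read, pooled normal-approximation tests at one-sided 0.05 (rates 50%, 25%, 25%; n = 90, 90, 45) give power 0.970 for Arm 1 vs Arm 3 and 0.889 for Arm 1 vs Arm 5, with a simulated min-test power of 0.871. Protocol Table 7 has 0.970, 0.889 and 0.871.

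**Inputs**
- Arm 6: 45 participants at 5% (SAP 1.4), so 45 × 0.05 = 2.25 expected responders.
- Treatment history: 40% not currently treated (protocol 4.1), so 18 and 27 participants.
- HBeAg: 40% of the not currently treated are expected to be positive. The share among suppressed participants is not given. At an assumed 25%, 0.40 × 0.40 + 0.60 × 0.25 = 0.31 overall, or 14 positive and 31 negative.
- Shares for other variables are not given; equal levels are assumed.

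**Chance of an Arm 6 cell with no responders**

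P = 1 − ∏ₖ [1 − (1 − p)^nₖ]. For treatment history at 5%: 0.95^18 = 0.397 and 0.95^27 = 0.250, so P = 1 − 0.603 × 0.750 = 0.55.

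| Arm 6 cells | p = 2% | p = 5% | p = 10% |
|---|---|---|---|
| Treatment history (18, 27) | 0.87 | 0.55 | 0.20 |
| HBeAg (14, 31) | 0.89 | 0.59 | 0.26 |
| Three equal levels (15 each) | 0.98 | 0.85 | 0.50 |
| Four equal levels (11 each) | >0.99 | 0.97 | 0.78 |

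**The stratification-factor model itself.** With two arm-by-factor interactions and no three-way term, the fit is the same as a separate main-effects fit within each arm. In 20,000 simulated trials per setting, with 20–40% of suppressed participants HBeAg-positive, Arm 6 separated (no finite maximum-likelihood estimate) in 68–71% of trials at 5%, about 93% at 2%, and 30–38% at 10%.

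**Why dropping the term restores convergence.** Without the interaction, Arm 6 is a problem only if it has no responders at all: 0.95^45 = 0.10. For functional cure this can fail too. Protocol 9.4.1.2 reports mean HBsAg seroclearance on NA below 1%. At 1%, 0.99^45 = 0.64, and if Arm 6 is in the model, removing the interaction does not help.

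**What the reduced model does.** Illustration with assumed counts:

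| | Subgroup A | Subgroup B |
|---|---|---|
| Control | 2/27 | 0/18 |
| Active | 8/54 | 18/36 |
| Observed risk difference | 0.148 − 0.074 = 0.07 | 0.500 − 0 = 0.50 |
| OR, interaction model, ordinary ML | fit fails | fit fails |
| OR, interaction removed | 9.86 | 9.86 |
| Fitted risk difference, interaction removed | 0.175 − 0.021 = 0.15 | 0.460 − 0.080 = 0.38 |
| OR, Firth, interaction kept | 1.9 | 37 |

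In this saturated example, Firth amounts to adding 0.5 to every responder and non-responder count. For A, (8.5/46.5)/(2.5/25.5) = 1.86; for B, (18.5/18.5)/(0.5/18.5) = 37. It converged in about 10 steps.

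**The case against.** The strongest reply is that little hangs on this. The analyses are exploratory, with 90% CIs and no multiplicity adjustment, and no primary or key secondary test changes. Raw rates by HBeAg status and treatment history can still be seen, since protocol 9.4.1 plans summaries by stratification factor. SAP 5.2.2.2.1 also has a separate homogeneity test, limited to the two stratification factors and the comparisons with control. The wording is permissive, and marking any reduced model on the plot would meet much of the risk. All of this stands, and it limits the weight of the point.

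Some stronger readings should be resisted.

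- **That the fallback makes effects equal across subgroups.** It does so only on the odds-ratio scale. The subgroup main effect stays in, so the plotted response estimates, and the differences in proportions that the estimand uses, still vary (0.15 and 0.38 above). The reduced model leaves heterogeneity untested; it does not report homogeneity.
- **That 0.55 or 0.59 is the chance that the fallback is used.** Software may return very large estimates with only a warning, and removal is optional.
- **That the phrase "exploration of the interaction terms using observed case data" drops participants whom the main estimand counts as non-responders.** The SAP does not define the term. It may mean only that values are not multiply imputed, so no shift in rates is shown.
- **That Sensitivity Estimator 1 shares the fallback.** Its model ("A logistic regression model on the primary efficacy endpoint using the 2 randomization stratification factors and interaction terms") has no removal rule and uses the main estimator's data and multiple imputation. The stratification-factor model in 5.3.6 has no fallback sentence either; only its other-subgroup models inherit it.

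**Conclusion.** The point holds in a limited form. SAP 5.2.5, and 5.3.6 by cross-reference for the other subgroups, permit removal of the term that answers the heterogeneity question, under conditions that the planning assumptions make likely and that the SAP says had already arisen. The probabilities rest on a 5% control rate, 45 participants in Arm 6, an assumed HBeAg mix and equal levels elsewhere. They fall at a 10% control rate (0.20 by treatment history) and rise at 2% (0.87). The consequence is an untested interaction and a common odds ratio behind the forest plot, in an exploratory analysis. It is worth correcting because the SAP already uses a method that avoids the choice.

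**What to change.** In SAP 5.2.5 and 5.3.6, state that the interaction models are fitted with Firth's penalised likelihood, as 5.2.2.1.1.1 already does for the MCP step. Specify profile penalised-likelihood 90% CIs and a penalised likelihood-ratio test of the interaction. Delete the sentence that allows the interaction to be removed.

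The data used for these models need not change, so no new rule for pooling over imputations is required.

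The cost is SAP wording and modest extra programming for the intervals and the test. Intervals in sparse cells will be wide, which reflects the information available. Firth also moves fitted rates away from zero: in the example, control subgroup B becomes 0.5/19 = 0.026 against 0 observed. Printing responders over participants beside each estimate would make this visible.

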5.3. Key Secondary Endpoint

5.3.1. Definition

The key secondary endpoint is the proportion of participants having HBsAg seroclearance 24 weeks after stopping all study interventions at Week 48. This endpoint will be called as “functional cure” at week 72 interchangeably in the rest of this document.

A participant will be defined as having achieved functional cure (FC) at Week 72 if he/she has:

- met the criteria for stopping NA treatment at Week 48, and
- had HBsAg seroclearance at Week 72 (i.e. 24 weeks after stopping all study interventions), and
- not required NA re-treatment between Weeks 48 and 72.

Seroclearance of HBsAg is defined as HBsAg level<LLOQ. It can be noted that a participant may achieve HBsAg seroclearance prior to Week 72, but the HBsAg level<LLOQ has to be shown at Week 72 to be counted as responder.

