The functional cure rate at Week 72 is defined as the proportion of participants with HBsAg seroclearance 24 weeks after completion of all study intervention at Week 48, including stopping NA treatment. It will be used to support the JNJ-3989 dose selection and the regimen selection. The same multi-step testing strategy as the one implemented for the primary efficacy endpoint (see Section 9.4.1.1), using MCP-Mod and additional treatment arms pairwise comparisons with NA control in a fixed sequence, as well as the min test approach separately for between-regimen comparisons, will be used for this key secondary endpoint. However, the comparisons with NA control in the testing strategy applied to this efficacy endpoint will be made against the NA historical control benchmark of 5%, instead of the study NA control arm (Arm 6).

To provide evidence of superior efficacy of the JNJ-3989+JNJ-6379+NA regimen against the JNJ-3989+NA and JNJ-6379+NA combination regimens, respectively, those tests will be performed at a one-sided 0.025 alpha level for regulatory consideration. This analysis aims to support the selection of the combination drug therapy to be studied in confirmatory studies.

Additionally, the functional cure efficacy endpoint will be summarized for the control Arm 6 with the point estimate paired with its 90% CI using the Clopper-Pearson exact method to assess the consistency with the assumed historical control value.

As a secondary analysis, this key secondary endpoint will be compared between intervention arms in a logistic regression model with factors for treatment arm, treatment status and HBeAg status at screening. The potential impact of each randomization factor will be assessed by

comparing the model with and without treatment-by-randomization interaction terms. Appropriate 90% CIs will be also calculated without multiplicity adjustment. Exploratory subgroup summaries will be displayed graphically in forest plots.

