5.3.2. Main Estimand of The Key Secondary Endpoint

Study Objective: To evaluate the efficacy of the study intervention 24 weeks off-treatment.

Scientific Question: in the adult population with chronic HBV infection

- a) what is the benefit of any of the JNJ-3989 doses (40mg, 100mg or 200 mg) (Arms 2-4) administered in combination with NA for 48 weeks in terms of functional cure 24 weeks after stopping all study interventions compared with historical control (5%)?
- b) what is the benefit of JNJ-3989 100 mg+JNJ-6379+NA (Arm 1) and JNJ-379+NA (Arm 5) for 48 weeks in terms of functional cure 24 weeks after stopping all study interventions compared with Historical Control (5%)?
- c) what is the benefit of JNJ-3989 100mg+NA with or without JNJ-6379 (Arm 1, 3) or JNJ-6379+NA (Arm 5) administered for 48 weeks in terms of functional cure 24 weeks after stopping all study interventions?

A) Study Intervention:

- Arm 1: JNJ-3989 (100 mg) + JNJ-6379 (250 mg qd) + NA

- Arm 2: JNJ-3989 (200 mg) + Placebo + NA
- Arm 3: JNJ-3989 (100 mg) + Placebo + NA
- Arm 4: JNJ-3989 (40 mg) + Placebo + NA
- Arm 5: Placebo + JNJ-6379 (250 mg qd) + NA
- Historical Control value of 5%

B) Study Population: HBeAg-positive and -negative chronic HBV-infected patients who are not being treated for their HBV infection (including treatment-naïve patients) or are virologically suppressed by being treated with NA.

C) Variable: Response status defined as participants who meet the criteria defining functional cure at Week 72 (responders) as in Section [5.3.1](#)

D) Intercurrent events:

- Treatment discontinuation prior to Week 48: if the participant discontinued treatment prior to Week 48 then s/he will be considered non-responder (composite strategy).
- Major protocol deviations affecting efficacy: [ATTACHMENT 1](#) identifies the deviations considered intercurrent event (in per protocol set 2 column [PP2]). Participants with such deviations and who have missing data for the endpoint will be considered as non-responders (composite strategy). For all other deviations not considered intercurrent events, the data are used regardless of the occurrence of major protocol deviations (treatment policy strategy).
- Deaths prior to Week 72 are handled in a composite strategy as participants who die prior to Week 72 will be considered as non-responders.
- NA re-treatment between Week 48 and 72: the participant will be counted as non-responder (composite strategy).

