5.4.4. NA Re-Treatment During Follow-Up

The number and proportion of participants who meet the criteria for NA re-treatment at any time during FU will be summarized descriptively by intervention arm. Only the subset of participants who meet the NA treatment completion criteria at any time during the study and actually stop NA treatment will be included in the analysis.

The proportion of participants who actually re-started NA treatment during the follow-up phase on the basis of the 'Study Drug Administration for ETV, TDF or TAF' CRF page will be summarized separately over time (e.g. FU Week12, 24, 48, etc.) by intervention arm.

Due to the Protocol Amendment #4 to update the criteria for NA re-treatment for participants who discontinued NA treatment at Week 48, the participants who met NA re-treatment criteria in follow-up will also be listed along with their respective criterion. The proportion of participants who met the criteria according to the flag on the CRF page of 'NA Re-treatment Criteria Assessment' during the follow-up phase was summarized over time by intervention arm prior to Protocol Amendment 4 approval.

A cross-tabulation of participants who actually re-started NA treatment (re-started/not restarted) versus participants who met the above criteria (met/not met) will be presented over time.

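### The Week 72 functional-cure scoring rule does not verify that NA was actually stopped, although the endpoint is stated as an off-treatment one

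*SAP*

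**What the plan says.** SAP 5.3.1 opens with the intended endpoint: "The key secondary endpoint is the proportion of participants having HBsAg seroclearance 24 weeks after stopping all study interventions at Week 48". It then lists three conditions for a responder:

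1. "met the criteria for stopping NA treatment at Week 48, and"
2. "had HBsAg seroclearance at Week 72 (i.e. 24 weeks after stopping all study interventions), and"
3. "not required NA re-treatment between Weeks 48 and 72"

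Protocol 9.4.1.2 defines the same endpoint as "HBsAg seroclearance 24 weeks after completion of all study intervention at Week 48, including stopping NA treatment".

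The main estimand in SAP 5.3.2 has four intercurrent events: treatment discontinuation before Week 48, selected major protocol deviations, death before Week 72, and NA re-treatment between Weeks 48 and 72.

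For NA stopping itself, Protocol 6.6 and SAP 1.2 say that participants who meet the criteria stop NA at Week 48. Protocol 6.6 has one exception. If ALT is at least 3x ULN at Week 44, but the rise is unrelated to HBV or ALT has fallen below 3x ULN by Week 48, completing NA is left to the investigator in consultation with the sponsor. SAP 5.2.1 handles the same situation differently: a qualifying ALT re-test makes the participant a responder on the completion criteria, with no mention of whether NA was stopped.

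**The concern.** The lead sentence describes an off-treatment outcome. The scoring conditions test three other facts: eligibility to stop NA, the HBsAg level at Week 72, and absence of re-treatment. Eligibility and stopping usually coincide, but nothing in the rule confirms that they did for a given participant.

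The endpoint supports dose and regimen selection (Protocol 9.4.1.2). For Arms 1 and 5 it is tested against a fixed 5%, so a miscounted case can only raise the observed rate relative to the benchmark. In the between-regimen comparisons miscounts could fall in either arm, and the direction of any effect is not determined.

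**Working it through.** The plan gives no figure for this point, so there is none to reproduce. The check follows one participant through the rule, compares other SAP sections, and then illustrates size.

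Step 1: one participant. At Week 44: HBV DNA below LLOQ, HBeAg-negative, HBsAg below 10 IU/mL, ALT at least 3x ULN. ALT is below 3x ULN on re-test before Week 48. NA is continued, which Protocol 6.6 permits. HBsAg is below LLOQ at Week 72.

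- Condition 1: met, through the re-test note in SAP 5.2.1.
- Condition 2: the laboratory part is met. The bracketed words are untrue of this participant, but they explain what Week 72 is taken to mean and are not set out as a separate test.
- Condition 3: met trivially, because NA that never stopped cannot be re-started.
- Intercurrent events in 5.3.2: none applies.
- Attachment 1: items 21 to 24 cover failure to re-start NA; no item covers failure to stop it. For deviations that are not intercurrent events, 5.3.2 uses the data as observed. For those that are, it imposes non-response only when endpoint data are missing.

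Result: the conditions, applied literally, score this participant as a functional cure.

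Step 2: the rest of the SAP treats meeting the criteria and stopping NA as separate facts.

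- 5.3.5, analysis 2, has its own item requiring that all study treatment was stopped.
- 5.4.1.2 checks the treatment-disposition CRF pages to confirm stopping.
- 5.4.3.3 counts the date of meeting the criteria whether or not treatment was then discontinued.
- 5.4.4 restricts its denominator to participants who "meet the NA treatment completion criteria at any time during the study and actually stop NA treatment".
- 5.4.1.1 (Week 96) has the same gap as 5.3.1.

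Step 3: size. Inputs: planned n = 90 (Arm 1) and 45 (Arm 5) from Protocol 9.2; benchmark 0.05 and exact one-sided test at 0.05 from SAP 5.3.2.1.1.2. Complete data are assumed. The p-value for r responders is P(X ≥ r) with X binomial(n, 0.05).

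| n | responders | rate | exact p | rejects |
|---|---|---|---|---|
| 90 | 9 | 10.0% | 0.036 | yes |
| 90 | 8 | 8.9% | 0.081 | no |
| 45 | 6 | 13.3% | 0.024 | yes |
| 45 | 5 | 11.1% | 0.073 | no |

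One participant weighs 1/90 = 1.1 points or 1/45 = 2.2 points, and one miscount at the boundary changes the decision.

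Next, assume a true off-treatment rate of 5% and a miscounted fraction q of the arm. The documents give no value for q; the range is an assumption. The chance of reaching the rejection threshold is P(X ≥ r) with X binomial(n, 0.05 + q):

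| q (assumed) | n = 90, r = 9 | n = 45, r = 6 |
|---|---|---|
| 0 | 0.036 | 0.024 |
| 1% | 0.091 | 0.051 |
| 2% | 0.178 | 0.092 |
| 3% | 0.293 | 0.148 |

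These are single-test figures that ignore the earlier steps of the fixed sequence. Under multiple imputation, SAP 5.3.2.1.4 uses an asymptotic standard error instead of the exact test, so they are illustrative only.

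**The case against.** The strongest reply is that stopping NA is already part of the endpoint. The lead sentence says so, condition 2 repeats it, and the objective and all three scientific questions in 5.3.2 are framed off treatment. For someone still on NA, Week 72 is not 24 weeks after stopping, so condition 2 read whole is not met. Meeting the criteria also normally triggers stopping. The compliant exception is narrow: raised ALT at Week 44, a lower re-test, the other three criteria met, NA continued, and HBsAg below LLOQ at Week 72. Finally, analysis 2 in 5.3.5, the checks in 5.4.1.2 and the follow-up NA exposure summary in 4.6 would show a material discrepancy.

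Most of this stands. A reader might infer that the definition admits on-NA clearance by design, or that the SAP departs from the protocol endpoint. The documents do not support either reading: the stated endpoint is the same in both, and the gap lies only in how it is scored. A reader might also infer that many participants were kept on NA after the post-treatment reactivation case in Protocol 2.3.3. The documents describe the response to that case as changes to monitoring and re-treatment criteria, and current Protocol 6.6 still has NA stopped when the criteria are met.

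The reply does not supply a scoring rule. Intent in a lead sentence leaves the programmer to choose, and analysis 2 does not replace the main estimator because it drops both the completion criteria and the fixed treatment duration.

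**Conclusion.** The point holds as an operational gap. SAP 5.3.1 states an off-treatment endpoint but does not verify that NA was stopped, and neither the intercurrent events nor Attachment 1 closes the gap. There is one protocol-compliant route to a miscount, the ALT re-test; the other is non-adherence to the stopping rule.

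The number of cases is unknown and probably small. The 1.1 and 2.2 points might be taken as an estimate of bias, but they are only the weight of one participant, and the 1% to 3% miscount rates are assumed. No bias is demonstrated. The point still merits correction because a single case can decide a borderline test against 5%, and because the SAP already applies the missing check in less important analyses.

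**What to change.** - In SAP 5.3.1, add a fourth condition: all study interventions including NA were stopped at Week 48, confirmed from the treatment-disposition and NA administration CRF pages. State the date tolerance.
- In 5.3.2, add an intercurrent event for participants who met the criteria but continued NA, and score them as non-responders. A new row in Attachment 1 would not be enough, because 5.3.2 imposes non-response on listed deviations only when endpoint data are missing.
- Make both changes in the Week 96 definition in 5.4.1.1.

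The cost is a few lines of text and a derivation from CRF pages that the SAP already uses in 5.4.1.2 and 5.4.4. Under SAP 1.5 the sponsor is fully unblinded at the primary analysis, and Amendment 2 (19 May 2022) refers to past interim analyses. The change should therefore be documented as a post-unblinding clarification that aligns the scoring rule with Protocol 9.4.1.2. It alters scoring only, not patient management.
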